5.3 Safety Monitoring

Data Safety Monitoring Board

An independent Data Safety Monitoring Board (DSMB) comprised of two pediatric neurosurgeons with relevant expertise in CM+SM, a biostatistician, a clinical ethicist, and a patient partner will

assess and monitor the safety of the trial. The purpose of the DSMB is to advise the funding agency (PCORI), the study Principal Investigator ([name]), and the Investigators Committee regarding the continuing safety of study participants and the continuing validity and scientific merit of the study. The DSMB is responsible for monitoring accrual of study subjects, adherence to the study protocol, assessment of data quality, performance of individual clinical sites, review of serious adverse events and other subject safety issues, and review of formal interim statistical analyses of treatment efficacy. The DCC will send reports relating to these topics to DSMB members 10 days prior to each DSMB meeting. Based on prospectively defined guidelines to be outlined in the DSMB charter, the DSMB should recommend whether or not to terminate enrollment in the study because of potential safety concerns or high evidence of efficacy. The DSMB will also have the option to recommend stopping the study due to low likelihood of finding an effect if the trial continues (futility), or if the risks/benefit ratio is not favorable. Each DSMB meeting will result in a summary report that will be provided to the Investigator Committee, PCORI, and each local IRB.

6. INTERVENTION DISCONTINUATION

For the purposes of this trial, the intervention is either of two technical variants of surgical decompression for CM+SM, PFD or PFDD. While it is possible that intra-operative factors that could influence a surgeon's plan to carry out the intended procedure (PFD or PFDD), this would be highly unlikely. Nevertheless, if the surgical technique is aborted or changed during the procedure, participants will be followed per study protocol with all associated clinical care and data collection.

7. STATISTICAL CONSIDERATIONS

7.1 General Design Issues

The Central Hypothesis of this proposal is that, compared with PFDD, PFD will result in fewer

surgical complications and thus less harm to patients within 12 months (± 2 months) of surgery. With a more favorable risk profile and non-inferior effect on clinical outcome and syrinx size compared with PFDD, PFD will be associated with superior QOL.

This study is designed as a cluster randomized controlled trial (C-RCT) of the two major neurosurgical treatments for CM+SM: posterior fossa decompression with duraplasty (PFDD) and extradural posterior fossa decompression (PFD). This design was chosen with input from site investigators (neurosurgeons) in order to obtain participation from a large number of pediatric neurosurgeons and reduce crossovers and non-participation resulting from physician bias. While there is inherent individual surgeon bias, clinical equipoise exists across the field; this is underscored by the participation of >50% of the pediatric neurosurgeons in the United States in this RCT and support of this study by the AANS, the CNS, and the Joint AANS/CNS Pediatric Section.

7.2 Sample Size and Randomization

7.2.1 Treatment Assignment Procedures

This study is designed as a cluster randomized controlled trial (C-RCT) of the two major neurosurgical treatments for CM+SM: posterior fossa decompression with duraplasty (PFDD) and extradural posterior fossa decompression (PFD). This design was chosen with input from site investigators (neurosurgeons) in order to obtain participation from a large number of pediatric neurosurgeons and reduce crossovers and non-participation resulting from physician bias. During extensive discussions with PRSRC investigators and patient partners, there was significant concern for selection bias due to crossovers and selective enrollment if individual patients were randomized, a known problem in surgical trials [33]. Site investigators felt that having their entire practice randomized to one technique would increase surgeon comfort and experience with that approach, thereby decreasing tendencies for biased enrollment. Consequently, individual PRSRC centers will be randomized to perform either PFDD or PFD. In this design, PRSRC centers will be serve as the unit of inference for comparing PFDD and PFD, and the cluster size is expected to be 6 patients per center (3 per center per year). For cluster randomization, a computer-generated randomization sequence will be generated independently by the study statistician. Overall sample size of 148 participants will be enrolled. Approximately 74 participants per procedure over the two years of enrollment.

Potential participants will be identified, screened, and recruited through the clinical practices of 36 participating PRSRC sties in addition to 7 other sites. In this trial, the randomization unit will be the PRSRC center; therefore, the same intervention will be used for all qualifying patients enrolled at each center. If a surgeon in a PRSRC center strongly believes that a patient should undergo a certain procedure (PFDD or PFD), the patient will not be randomized. Effective randomization will occur through the random distribution of patients to centers employing each procedure (PFDD and PFD).

Aim 1: Power Calculations

For the purpose of sample size estimation, data from in the Park-Reeves Syringomyelia Research Consortium (PRSRC) were analyzed (ambispective enrollment, n=589 subjects with complete data); specifically, surgical complications ≤ 12 months were used to calculate the sample size. In this dataset, surgical complications were noted in 17.8% of PFDD cases and 2.7% of PFD cases. This is consistent with reported values from a recent meta-analysis, where the rates for CSF-related complications for PFDD and PFD were 18.5% and 1.8%, respectively [27], as well data reported in case series [17, 25] and a systematic review [42]. We expect to observe a similar difference in PFDD versus PFD cases in the proposed study. Because of the clustered randomized nature of the trial, the intraclass correlation coefficient (ICC) should be taken into account. The ICC is defined as the proportion of the between cluster (PRSRC center) variation to the total variation. Since the cluster sizes are small (6 per PRSRC center), and we have a large number of centers available for enrollment (47 total), the effect of ICC on sample size will be small. Thus, using the PRSRC values of 17.8% for PFDD and 2.7% for PFD, and assuming equal number of subjects per group and twosided type I error rate of 0.05, to reach 90% power, 36 centers averaging 6 subjects per center will be required for the trial assuming the ICC is 0.05. To account for 2% dropout rate, we originally planned to recruit 40 centers with a cluster size averaging 6 subjects with overall sample size of enrolled patients of 240 patients, approximately 120 patients per procedure over the two years of enrollment.

Aim 1: Sample Size Recalculation (November 29, 2017)

The original sample size calculation was performed based on surgical complication rates (≤ 12 months) from Park-Reeves Syringomyelia Research Consortium (PRSRC) estimates (17.8% in PFDD and 2.7% in PFD cases). We originally did not have an estimate for the ICC. Based on the literature, we assumed ICC of 0.05 in our calculations [43]. The overall sample size of enrolled patients would be 240 patients, approximately 120 patients per procedure over the two years of enrollment.

In preparation for our PFD trial annual meeting on November 29, 2017, we performed a sample size re-calculation, using the ICC observed from the 47 patients enrolled in the study and for which complete data was available as of November 28, 2017. It should be noted that the data was only used to calculate the ICC; no interim analyses were performed. The ICC based on the first enrolled 47 patients was 0.000059, much smaller than what was assumed (0.05) for the original sample size calculation. However, we expect this ICC estimate to change with more enrollments.

Enrollment in the trial has increased over time and continues to do so (for example, 10 patients were enrolled in both November and December, 2017 and the total trial enrollment is now 83). However, when calculated at the time of the annual meeting at the end of November 2017, the average accrual rate, calculated over the entire 19-month period of the study, was 6 patients per month. Thus, using the conservative projection of 6 patients per month over the course of an enrollment extension ending 12/1/2018, we expect the total number of subjects to be at least 145 (73 + 12 x 6). (73 was the total enrollment when these calculations were made at the end of November; however, as noted above, 10 patients were recruited in December.)

Based on the enrolled 47 patients in the database with complete data as of 11/28/17, the average cluster size is 2.9. If we assume each center enrolls 3 more patients over the enrollment extension, the average cluster size increases to 5.9. With the current ICC estimate of 0.01 and using the original estimates for the complication rates (17.8% in PFDD and 2.7% in PFD), with the projected sample size of 145, we can still reach 84% power by enrolling patients from 24 centers with an average cluster size of 6 (144 subjects total). The same power level can also be achieved by enrolling patients from 30 centers with an average cluster size of 5. To account for a potential 2% loss to follow up rate, we planned to recruit 148 subjects total (74 per group) over the entire trial enrollment period.

It should be noted that it is assumed that the average cluster size is 6 in all centers for these calculations. The design effect (DE) concept is used in cluster randomized trials to inflate the sample size of the study, compared to the traditional randomized trials [44]. When cluster size is fixed, $DE = 1 + [(m - 1) \times ICC]$; where m is the average cluster size and ICC is the intraclass correlation coefficient. In other words, the sample size of the study can be calculated by traditional methods, and should be multiplied by the DE. Under the assumption that m = 6 and ICC = 0.01, DE becomes 1.05. To compare 17.8% vs 2.7% surgical complication rates for a (*not clustered*) randomized trial, with 84% power, and 0.05 type I error rate, we would need to enroll 136 patients total. This is also listed in the sample size calculator above under the "unadjusted box". For a DE value of 1.05, this sample size should be multiplied by 1.05 to find the sample size of a cluster randomized trial to reach same power. Therefore, the sample size of the clustered randomized trial would be 136 x 1.05 = 142.8 ~143.

The variable cluster size is common in cluster randomized trials. Eldridge et al considered the effect of variable cluster size on the sample size calculation for cluster randomized trials [45]. They showed that the DE value can be calculated for variable class sizes. DE' = $1 + {(cv^2+1) m - 1} x$ ICC; where cv is the coefficient of variation of cluster sizes (standard deviation of cluster sizes divided by the mean cluster size). The cv is 1.08 for our study. If we use the current average cluster size of m = 2.9, DE' becomes 1.06. In other words, the sample size of the study should be inflated to 136 x 1.06 = 144.16~145 to reach 84% power. This assures us that our planned sample size of 145 patients will allow us to reach 84% power even if our cluster sizes will not be fixed at 6.

It should be noted that, as of March 6th 2018, only 1 of 100 enrolled patients was lost to followup. However, to account for a potential 2% loss to follow up on the 145 subjects needed (72 per group), we will recruit 148 subjects total (74 per group) over the entire trial enrollment period, which is proposed to be extended to December 31, 2018.

Aim 2: Non-Inferiority Margins and Power

The non-inferiority margins for this trial were determined in conjunction with a panel of experts on CM+SM and related treatment (the Park-Reeves investigators), our non-physician stakeholder partners, and our patient partners, [name], [name], [name], [name], [name], [name], and [name]. Using a clinical, Delphi-type approach [46] for the complex measure of clinical improvement, the research team agreed upon a non-inferiority margin of no more than 20% lower response for PFD from the PFDD group. The clinical improvement rate (the improvement from baseline to 12 months) for the PFDD group was provided as 78.6% in the Durham study [27]. Thus, with the sample size of 72 subjects per group (after an assumed 2% dropout), we can conclude the non-inferiority of the PFD to PFDD with a margin of 0.17 units (α =0.05, 80% power). This corresponds to clinical improvement rate of 61.6% in the PFD group. It was shown in the Durham study that the clinical improvement following PFD was 64.6%.

Determine if PFD provides non-inferior clinical improvement compared to PFDD (Non-inferiority Design)							
Outcome	PFDD	PFD	Data Source	Non-inferiority Margin	α-level	Subjects per group	Power
Clinical Improvement	44/56 (78.6%)	51/79 (64.6%)	Durham [27]	0.17	0.05	72	80%

For these calculations, the drop-out rate is assumed to be 2%, and the one-sided type I error rate is 0.05.

After determination with the Delphi method, the non-inferiority margin was subsequently confirmed as appropriate using Rothman's 95-95 approach [47, 48] and the FDA guidelines for selecting the non-inferiority margin for non-inferiority clinical trials [49]. Using these methods, the non-inferiority margin was estimated using the effect of the standard treatment (PFDD) from Durham's meta-analysis [27], with the lower 1-sided 95% confidence interval for the random-effects meta-analysis calculated to be used as a non-inferiority margin. When the data from the PFDD group from the Durham study was used for the clinical improvement outcome, the 95% lower 1-sided confidence interval from the random effects model was calculated as 0.611. In our proposal, we defined the non-inferiority margin as the difference between the clinical improvement rates in the PFDD and PFD groups ($\pi_{PFDD} - \pi_{PFD}$). For the clinical improvement outcome, this corresponds to the non-inferiority margin of 0.786 – 0.611 = 0.175 units. Therefore, our

recommended non-inferiority margin of 0.175 units for the clinical improvement outcome is consistent with the FDA-recommended largest acceptable non-inferiority margin of 0.175 units.

In contrast to clinical improvement, syrinx regression is an objectively measurable and easily quantifiable outcome. It is measured by comparing syrinx size on MRI scans obtained before and after surgery. When the effective sample size is 68 subjects per group, and assuming 89.1% syrinx regression rate in the PFDD group [27], the non-inferiority margin is 0.135 units to reach 81% power. A non-inferiority margin of 0.135 units represents no more than 13.5% reduction from the PFDD group in terms of syrinx regression. Note that a one-sided type I error rate of 0.05 was assumed, and the 'Two group test of equivalence in proportions' option in nQuery Advisor was used for the sample size calculations.

Determine if PFD provides non-inferior syrinx regression compared to PFDD (Non-inferiority Design)							
Outcome	PFDD	PFD	Data Source	Non-inferiority Margin	α-level	Subjects per group	Power
Syrinx Regression	261/293 (89.1%)	31/38 (81.2%)	Durham [27] and PRSRC	0.135	0.05	72	81%

For these calculations, the drop-out rate is assumed to be 2%, intra-class correlation coefficient is 0.05, and the onesided type I error rate is 0.05.

Aim 3: Power Calculations

Based on preliminary data using the Chiari Health Index in Pediatrics (CHIP)[50], we observed a 0.12±0.16 unit improvement in Quality of Life (QOL) scores following PFDD. Our sample size of 72/group (effective sample size of 68/group) will provide 82% power to detect a 0.20±0.16 unit improvement in CHIP QOL scores following PFD (α =0.05). Both from an analytical standpoint and from the view of PRSRC investigators and our patient partners, this value represents both a significant and meaningful increase in QOL

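### The check that unequal centre sizes leave 84% power at 145 patients uses the interim mean of 2.9 per centre, not the 5–6 behind the 84%; at 6 per centre, power is about 82–83.5%

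*SAP*

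**What the plan says.** SAP 7.2.1, under the Aim 1 recalculation of November 29, 2017, projects a mean of 5.9 patients per centre by the end of enrolment and says "we can still reach 84% power by enrolling patients from 24 centers with an average cluster size of 6". It gives 30 centres averaging 5 as an equivalent layout. The fixed-size design effect uses a mean of 6 and an ICC of 0.01, giving 1.05 and 143 patients from an unclustered requirement of 136.

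The next paragraph allows for unequal sizes with DE' = 1 + {(cv² + 1)m − 1} × ICC and cv 1.08. Here the mean changes: "If we use the current average cluster size of m = 2.9". The plan obtains DE' = 1.06, multiplies 136 by it to reach 145, and concludes: "our planned sample size of 145 patients will allow us to reach 84% power even if our cluster sizes will not be fixed at 6".

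Protocol 9.5 contains the same check and the same conclusion.

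**The concern.** The design effect grows with the mean number of patients per centre at the end of the trial. The check makes two changes at once. It brings in the cv, which raises the design effect, and it halves the mean, which cancels most of that rise. The result looks as though unequal centre sizes cost almost nothing.

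A mean of 2.9 is also incompatible with the layouts given for the 84%: 145 / 2.9 = 50 centres, against 24 or 30 in the power statement and 43 to 48 in the various site counts in the two documents.

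At stake is whether a reader can rely on the one statement in the plan about unequal centre sizes.

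**Working it through.** **Inputs.** From SAP 7.2.1: complication rates 17.8% and 2.7%; two-sided 0.05; unclustered total 136; ICC 0.01; cv 1.08; mean 2.9 (interim), 5.9 (projected), 6 or 5 (power statement); 145 evaluable patients.

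**Power formula.** Two proportions with pooled variance under the null and no continuity correction:

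power = Φ[(0.151 − 1.96 √(0.18399/n)) / √(0.17259/n)], with n = 145 / (2 × DE').

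Here 0.151 = 0.178 − 0.027; 0.18399 = 2 × 0.1025 × 0.8975; and 0.17259 = 0.178 × 0.822 + 0.027 × 0.973.

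**Reproducing the plan.**
- Unclustered, 68 per arm: 83.5%. The 136 is consistent with the stated 84% after rounding.
- Fixed size, m = 6: DE = 1 + 5 × 0.01 = 1.05; 136 × 1.05 = 142.8; power at 145 is 84.1%.
- The plan's check, m = 2.9: cv² + 1 = 2.1664; DE' = 1 + (2.1664 × 2.9 − 1) × 0.01 = 1.053; power at 145 is 84.0%. The plan writes 1.06, which rounds up and so errs on the safe side.

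**The same check at the planned mean.** With m = 6 and cv 1.08, DE' = 1 + (2.1664 × 6 − 1) × 0.01 = 1.120. Then 136 × 1.120 = 152.3, so 153 patients. At 145, n = 64.7 per arm, and power = Φ[(0.151 − 1.96 × 0.0533) / 0.0516] = Φ(0.90) = 81.6%. If 136 patients are taken to give exactly 84%, this becomes 82.2%.

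**Letting cv move with the mean.** If 1.08 is the interim value, the interim SD is 1.08 × 2.9 = 3.13. If every centre then adds exactly 3 patients, the SD is unchanged and cv = 3.13 / 5.9 = 0.53. Then DE' = 1 + ((0.53² + 1) × 5.9 − 1) × 0.01 = 1.066, 136 × 1.066 = 145, and power at 145 is 83.5%.

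| Layout | m | cv | ICC | DE' | N needed | Power at 145 |
|---|---|---|---|---|---|---|
| Plan's check (50 centres) | 2.9 | 1.08 | 0.01 | 1.053 | 144 | 84.0% |
| 48 centres | 3.0 | 1.08 | 0.01 | 1.055 | 144 | 83.9% |
| 43 centres | 3.4 | 1.08 | 0.01 | 1.063 | 145 | 83.6% |
| 30 centres | 5 | 1.08 | 0.01 | 1.098 | 150 | 82.4% |
| 24 centres | 6 | 1.08 | 0.01 | 1.120 | 153 | 81.6% |
| 24 centres | 6 | 0.9 | 0.01 | 1.099 | 150 | 82.4% |
| 24 centres | 6 | 0.7 | 0.01 | 1.079 | 147 | 83.0% |
| 24 centres | 6 | 0.53 | 0.01 | 1.067 | 145–146 | 83.5% |
| 24 centres | 6 | 1.08 | 0.05 | 1.600 | 218 | 66.4% |
| 24 centres | 6 | 0.53 | 0.05 | 1.334 | 182 | 74.4% |

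**Small-sample correction (assumption only).** Replacing 1.96 by the t value on 22 degrees of freedom (24 centres, cv 1.08, ICC 0.01) gives about 78–80%, depending on the variance form. A simulation of 24 unequal centres with a cluster-level variance and the same t value gave 83.6%, so this figure depends on the method.

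**The case against.** **The cv may be an interim value too.** The plan gives 1.08 for the study next to the interim mean. Moving the mean to 6 while keeping 1.08 may therefore mix final and interim values. This stands: 153 patients and 82% are one end of a range, and even filling brings the requirement back to about 145. But even filling is the favourable end. A mean of 2.9 over 47 patients is about 16 centres (47 / 2.9), so reaching 24 needs centres outside that dataset, and the plan states no lower cv.

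**Many centres may enrol.** With 43–48 centres the mean is 3.0–3.4 and about 84% holds. This also stands, but the plan attaches its 84% to 24 or 30 centres.

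**Stronger readings that the documents do not support.**
- A reader might infer that the planned small-sample correction lowers power to 78–80%. The SAP allows either corrected GEE or random-effect logistic regression, and names no correction and no degrees of freedom.
- A reader might infer that this check justified the reduction from 240 to 148. The 145 comes from projected accrual (73 + 12 × 6) and the 84% from the fixed-size calculation; the unequal-size paragraph is an added check. In Protocol 9.5, 148 is a minimum, with up to 238 allowed.
- A reader might infer that the plan took the near-zero interim ICC at face value. It reports "The ICC based on the first enrolled 47 patients was 0.000059", expects that to change, and calculates with 0.01. At the observed value, power is about 86% whatever the mean size.

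**Conclusion.** Wrong as written, and modest in size. The check behind the assurance uses a mean that belongs to a 50-centre trial, while the 84% it defends belongs to 24 centres of 6 or 30 of 5. At 24 centres averaging 6 and ICC 0.01, 145 patients give about 82% power if the final cv is 1.08 and about 83.5% if it is about 0.53. The requirement is 145 to 153 patients. The loss is about 0 to 2 points.

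This rests on the plan's complication rates, its unclustered 136, its design-effect formula and ICC 0.01. If the ICC were 0.05, the value first assumed, power at 24 centres averaging 6 would be about 66–74% over the same cv range. That is sensitivity to the ICC and a separate matter from the choice of mean. The documents do not support a conclusion that the trial is seriously underpowered, or that 153 patients are definitely required.

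**What to change.** In SAP 7.2.1 and Protocol 9.5, recompute DE' with m = 145 divided by the number of enrolling centres, and with the cv of the final centre sizes. Replace the sentence that gives the assurance with a power statement that names m, cv and ICC, for example:

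> Power with 145 evaluable patients is about 82–83.5% at 24 centres averaging 6 (ICC 0.01, cv 1.08 to 0.53); about 84% at 43–48 centres (ICC 0.01, cv 1.08); and about 66–74% at 24 centres averaging 6 if the ICC is 0.05, over the same cv range.

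If a loss from the small-sample correction is quoted, label it as an illustration and state the assumed degrees of freedom, or name the correction in the SAP first.

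The cost is wording only: no new data and no change to design or analysis. The stated power becomes slightly less favourable.

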#### Aim 2: Non-Inferiority Margins and Power

The non-inferiority margins for this trial were determined in conjunction with a panel of experts on CM+SM and related treatment (the Park-Reeves investigators), our non-physician stakeholder partners, and our patient partners, [name], [name], [name], [name], [name], [name], and [name]. Using a clinical, Delphi-type approach [46] for the complex measure of clinical improvement, the research team agreed upon a non-inferiority margin of no more than 20% lower response for PFD from the PFDD group. The clinical improvement rate for the PFDD group was provided as 78.6% in the Durham study [27]. Thus, with the sample size of 72 subjects per group (after an assumed 2% dropout), we concluded non-inferiority of the PFD to PFDD with a margin of 0.17 units ( $\alpha$ =0.05, 80% power). This corresponds to clinical improvement rate of 61.6% in the PFD group. It was shown in the Durham study that the clinical improvement following PFD was 64.6%.

Determine if PFD provides non-inferior clinical improvement compared to PFDD (Non-inferiority Design)							
Outcome	PFDD	PFD	Data Source	Non-inferiority Margin	α-level	Subjects per group	Power
Clinical Improvement	44/56 (78.6%)	51/79 (64.6%)	Durham [27]	0.17	0.05	72	80%

For these calculations, the drop-out rate is assumed to be 2%, and the one-sided type I error rate is 0.05.

After determination with the Delphi method, the non-inferiority margin was subsequently confirmed as appropriate using Rothman's 95-95 approach [47, 48] and the FDA guidelines for selecting the non-inferiority margin for non-inferiority clinical trials [49]. Using these methods, the non-inferiority margin was estimated using the effect of the standard treatment (PFDD) from Durham's meta-analysis [27], with the lower 1-sided 95% confidence interval for the random-effects meta-analysis calculated to be used as a non-inferiority margin. When the data from the PFDD group from the Durham study was used for the clinical improvement outcome, the 95% lower 1-sided confidence interval from the random effects model was calculated as 0.611. In our proposal, we defined the non-inferiority margin as the difference between the rates. For the clinical improvement outcome, this corresponds to the non-inferiority margin of 0.786 - 0.611 = 0.175 PCORI CER-1503-29700

Version 6 March 01, 2021

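### The 80% and 81% power for Aim 2 assume equal true PFD and PFDD rates, which neither document states; at the lower PFD rates printed in the same rows, power is about 11% and 24–26%

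*SAP*

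**What the plan says.** The Aim 2 power statements are in SAP section 7.2.1 and Protocol section 9.5, in each case under Aim 2: Non-Inferiority Margins and Power.

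- **Clinical improvement.** The PFDD rate "for the PFDD group was provided as 78.6"%. With 72 per group the SAP says "we can conclude the non-inferiority of the PFD to PFDD with a margin of 0.17 units", and the protocol says "we concluded non-inferiority of the PFD to PFDD with a margin of 0.17 units". The table footnote says that "the one-sided type I error rate is 0.05". The text equates the margin with a PFD rate of 61.6% and then reports that, in the cited meta-analysis, "the clinical improvement following PFD was 64.6"%. The table row shows 44/56 (78.6%) for PFDD, 51/79 (64.6%) for PFD, 72 per group and 80% power.
- **Syrinx regression.** With an effective 68 per group and 89.1% for PFDD, "the non-inferiority margin is 0.135 units to reach 81% power". The text adds: "Note that a one-sided type I error rate of 0.05 was assumed". The row shows 261/293 (89.1%) for PFDD, 31/38 (printed as 81.2%) for PFD, 72 per group and 81% power. Its footnote gives an ICC of 0.05.

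Neither document gives the true PFD rate, or the true difference, at which power was calculated. SAP 7.5 fixes the analysis margins at 0.17 and 0.135 and compares a one-sided confidence interval for the rate difference with them.

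**The concern.** Non-inferiority power depends heavily on the true difference assumed. Each row places a PFDD rate, a lower PFD rate, a margin and a power side by side, so a reader will naturally take the power to apply at the two rates shown. The printed PFD rates use up most of the margin: 14.0 of 17 points for clinical improvement and 7.9 of 13.5 for syrinx regression.

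The rest of the plan encourages that reading. Aim 1 is powered at the consortium's historical rates for both operations (17.8% and 2.7%). Aim 3 names its alternative (0.20 against 0.12 CHIP units). Only Aim 2 prints a historical PFD rate without saying which PFD rate was used.

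Non-inferior efficacy is part of the central hypothesis, and SAP 1.2 makes clinical symptoms and syrinx regression the primary outcomes for Aim 2. A reader who takes 80% at face value would credit a missed margin with more information than the design provides if PFD is somewhat less effective.

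**Working it through.** **Method.** Non-inferiority of two proportions, unpooled normal approximation, one-sided 0.05:

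power = Φ[(M − (pC − pT))/SE − 1.645], with SE = √{[pC(1 − pC) + pT(1 − pT)]/n},

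where pC is the PFDD rate, pT the true PFD rate, M the margin and n the number per group. All inputs come from SAP 7.2.1.

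**Step 1: reproduce the stated figures with pT = pC.**

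- Clinical, n = 72: SE = √(2 × 0.786 × 0.214/72) = 0.0684; power = Φ(0.17/0.0684 − 1.645) = 80.0%.
- Syrinx, n = 68: SE = √(2 × 0.891 × 0.109/68) = 0.0534; power = Φ(0.135/0.0534 − 1.645) = 81.1%.

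Solving for sample size under equality returns exactly 72 and 68 per group. A one-sided 0.025 level does not match: it gives 70.1% (n = 72) and 71.4% (n = 68). A superiority test of 78.6% against 61.6% does not match either (about 72%).

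**Step 2: use the PFD rates printed in the rows.**

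- Clinical, 78.6% v 64.6%: SE = 0.0742; power = Φ(0.03/0.0742 − 1.645) = 10.7%.
- Syrinx, 89.1% v 81.2%, n = 68: SE = 0.0606; power = Φ(0.056/0.0606 − 1.645) = 23.5%, or 24.4% at the table's n = 72. The fraction 31/38 is 81.6%, not 81.2%; using it gives 25.7% (n = 68) or 26.6% (n = 72).

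**Step 3: a 5-point true deficit.**

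- Clinical, 78.6% v 73.6%: SE = 0.0710; power = Φ(0.12/0.0710 − 1.645) = 52%.
- Syrinx, 89.1% v 84.1%: SE = 0.0583; power = Φ(0.085/0.0583 − 1.645) = 43%.

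| True PFD rate | Clinical (n = 72) | Syrinx (n = 68) |
|---|---|---|
| Equal to PFDD | 80% | 81% |
| 5 points lower | 52% | 43% |
| As printed in the row | 11% | 24% (26% at 31/38) |
| At the margin (61.6% / 75.6%) | 5% | 5% |

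**Step 4: robustness at the printed rates.** A Farrington–Manning variance gives 10.8% (clinical, n = 72) and 22.8% (syrinx, n = 68). Exact enumeration gives 10.9% and 24.8%. Clinical power is 12.0% with margin 0.175, 20.1% with the 20-point limit from the Delphi exercise, and 13.0% with 119 per group. At the printed rates, about 2,727 per group would be needed for 80% power (clinical) and 507 for 81% (syrinx).

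**Step 5: design effect.** With the plan's formula 1 + (m − 1) × ICC and m = 6:

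- ICC 0.05, as in the syrinx footnote: 1.25, so 72/1.25 = 57.6 effective per group. Syrinx power is 75% at equal rates and 21% at the printed rates.
- ICC 0.01: 1.05, so 72/1.05 = 68.6. The effective 68 therefore fits an ICC near 0.01, not the footnote's 0.05.
- The clinical 80% uses 72 with no design effect. With 1.05 it would be 78.3% at equal rates.

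**Step 6: both outcomes.** At equal rates, 0.80 × 0.81 = 0.65 if the outcomes are independent. Positive correlation would raise this.

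**The case against.** The best defence is that nothing was calculated wrongly. A zero true difference is the usual planning assumption for non-inferiority, and the stated powers reproduce under it. The PFD rates sit beside a data-source column, no sentence uses them as design inputs, and the syrinx text takes only the PFDD rate as an assumption. All of this stands, and it makes the defect one of disclosure. It does not remove the defect, because the equal-rates assumption has to be inferred by back-calculation and the figures next to it point elsewhere.

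The historical gaps are also imprecise. Crude 95% intervals are about −1 to 29 points for 44/56 v 51/79, and about −5 to 20 for 261/293 v 31/38. Protocol Table 2 reports p = 0.12 for the pooled clinical difference and covers Chiari malformation with or without syrinx, a wider population than the trial's. This stands too: 11% and 24% are conditional on those rates.

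Further, the SAP's binary clinical score is averaged over symptoms and visits, so a binomial model may not fit the analysed endpoint. That is fair, but it applies equally to the plan's own 80%.

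Finally, a reader might infer that 64.6% is cited as reassurance because it lies above 61.6%. The text only reports the two numbers in sequence and draws no such conclusion, so that motive should not be attributed to it.

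**Conclusion.** The power figures of 80% and 81% apply when the true PFD rate equals the PFDD rate; power would be higher if PFD were better and falls quickly if it is worse. Neither document says this, and the rows do not have the stated power at the rates they list: there it is about 11% for clinical improvement and 24–26% for syrinx regression. These results rest on the documents' own margins, sample sizes and one-sided 5% level, and on a binomial model.

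Two stronger readings are tempting and are not supported. The first is that the sample-size arithmetic is wrong; it reproduces. The second is that Aim 2 will fail about nine times in ten on clinical improvement; that would require one imprecise estimate from 79 historical patients to be the truth in this trial. Nor should the 65% joint figure be quoted without its conditions, which are equal rates and independent outcomes.

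The point should be fixed as a matter of disclosure. It does not call any margin or test into question.

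**What to change.** In SAP 7.2.1 and Protocol 9.5, under Aim 2:

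1. State that 80% and 81% assume equal true rates in the two groups.
2. Label the PFD rates in the tables as historical data and not design inputs, and reconcile 31/38 with the printed 81.2%.
3. Add the power at the printed PFD rates (about 11% and 24%; about 26% if 31/38 is used) and at a 5-point deficit (about 52% and 43%).
4. State the design effect used for each row. The clinical row applies none. For syrinx regression, reconcile 68 effective per group with the footnote's ICC of 0.05, which with 6 per center gives about 58 effective per group and about 75% power at equal rates.
5. If a joint figure is given, say that about 65% assumes equal rates and independent outcomes.

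A sentence saying that an interval crossing the margin is reported as non-inferiority not shown is optional, since SAP 7.5 already implies it.

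The cost is wording in two documents and less favourable stated figures. No margin, test, sample size or patient is affected.
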